The following imputation rules in will be used for partial or missing death dates.

- If death year and month are available but day is missing:
 - If yyyymm for the date last known to be alive equals yyyymm for death date, set death date to the day after the date last known to be alive.
 - If yyyymm for the date last known to be alive is less than the yyyymm for death date, set death date to the first day of the death month.
 - If yyyymm for the date last known to be alive is greater than yyyymm for death date, assume death date is in error, do not impute and censor the subject survival time.
- If month and day are missing and year of death is known:
 - If yyyy for the date last known to be alive equals yyyy for death date, set death date to the day after last known to be alive date.
 - If yyyy for the date last known to be alive is less than yyyy for death date, set death date to the first day of the death year.
 - If yyyy for the date last known to be alive is greater than yyyy for death date, assume death date is in error, do not impute and censor the subject survival time.
- If a death date is totally missing:
 - Set death date to the day after the date last known to be alive. If the date last known to be alive is a partial date, set it to the first day of the month last known to be alive or first day of the year last known to be alive if month is also missing.

Outliers will be identified during the data management and data analysis process, but no sensitivity analyses will be conducted. All data will be included in the data analysis.

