6.2.5 Efficacy Endpoint: OS

Overall Survival (OS), defined as the time from the first dose of study treatment until death from any cause.

OS in months will be calculated as: (date of death from any cause - date of first dose + 1)/30.4375. Patients who are known alive as of their last known status will be censored at the date

of their last known to be alive. OS for patients will be summarized using 25th, 50th (median), and 75th percentiles with associated 2-sided 90% CIs, as well as percentage of censored observations. The median will be estimated by using the Kaplan-Meier method and corresponding 2-sided 90% CI using Brookmeyer and Crowley methodology (using log-log transformation). Number and percent of survival subject at 1 year will be estimated. The detailed censoring rules are displayed in [Table 11](#).

Table 11 Censoring Rules for OS

Situation	Outcome	Date of Progression or Censoring	Event Description/ Censoring Reason
Death before data cutoff	Event	Date of death	Death
Death after data cutoff	Censored	Date of data cutoff	Alive on or before data cutoff
No death before data cutoff	Censored	Date subject last known to be alive	Alive on or before data cutoff
Discontinued from study without death prior to data cutoff	Censored	Date subject last known to be alive	Discontinued from study

By-subject listings will be provided for target lesion, nontarget lesion, new lesion, and tumor response assessment. A by-subject listing of subsequent anti-cancer treatment will also be provided. By-subject listings for the efficacy endpoints above will also be provided.

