ADA Sampling		Refer to Protocol Table 4							Blood samples will be collected for ADA analyses at the time points specified and submitted to the central laboratory	

Phase 1b										
Study Phase	Screening	Cycle 1 (21 Days)				Subsequent Cycles* (21 Days)	EOT Follow-Up	LTFU	Notes	
Cycle Day	Screening	D1	D2	D4	D8	D15	D1	28 and 100 Days Post Last Dose		
Window (Days)	-28			± 1	± 1	± 1	± 3	± 7	± 14	
Tumor Tissue Biopsy	X						X	X		In dose exploration and expansion, pre- and on-treatment fresh biopsies will be mandatory at screening (prior to treatment) and prior to the Cycle 3 Day 1 dose, from the same lesion where feasible. An additional optional biopsy will be requested at the Day 28 EOT visit from patients who have documented disease progression.
Study Drug Dosing										FPT155 will be administered over approximately 60 minutes by IV infusion Q3W. Patients may continue receiving study treatment Q3W at the investigator's discretion until any of the protocol-specified treatment discontinuation criteria are met. For FPT155 + pembrolizumab cohorts, pembrolizumab will be administered 30 minutes after completion of the FPT155 IV infusion at a dose of 200 mg by IV infusion. If one study drug is discontinued, the other may be administered for up to 12 months or until protocol-specified discontinuation criteria are met.
Survival Assessment										
Survival Assessment								X		Patients will undergo LTFU for survival by clinic visit or by telephone approximately every 3 months ± 14 days after the Day 28 EOT visit, or until death, loss to follow-up, withdrawal of consent, or study termination by the Sponsor (whichever occurs first).

Abbreviations: ADA = anti-drug antibody; AE = adverse event; CR = complete response; CRS = cytokine release syndrome; CT = computed tomography; DLT = dose limiting toxicity; ECG = electrocardiogram; ECOG = Eastern Cooperative Oncology Group; EOT = end of treatment; IV = intravenous; HBsAG = hepatitis B surface antigen; HCV RNA = hepatitis C virus ribonucleic acid; LTFU = long-term follow-up; MRI = magnetic resonance imaging; PD = pharmacodynamic; PK = pharmacokinetic; PR = partial response; Q3W = every 3 weeks; RECIST = Response Evaluation Criteria in Solid Tumors; WOCBP = women of childbearing potential.

* There is a ± 3-day window for subsequent cycles after Cycle 1

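### With the death date missing and the last-alive date partial, SAP 5.2 imputes death with no lower bound, so death can precede a documented visit and OS can be zero or negative

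*SAP*

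**What the plan says.** SAP 5.2 (Handling Dropouts and Missing Values) has separate rules for death dates missing the day, missing day and month, and missing altogether. In the last case the instruction is to "set death date to the day after the date last known to be alive". The same bullet goes on to deal with an incomplete last-alive date: "If the date last known to be alive is a partial date, set it to the first day of the month". When only the year is known, 1 January of that year is used instead.

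SAP 6.2.5 then computes survival: "OS in months will be calculated as: (date of death from any cause - date of first dose + 1)/30.4375". Neither that section nor its censoring table (Table 11) sets a minimum.

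Other dates in SAP 5.2 are bounded. Imputed stop dates for adverse events and medications may not run past end of study or death. Partial adverse-event start dates can default to Study Day 1 when the eCRF flag supports it (Table 8). A partial death date that conflicts with the last-alive month or year is treated as an error and the patient is censored. The branch for a wholly missing death date has no comparable limit or check.

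**The concern.** Moving a partial date back to the first of the month or year is harmless only if nothing is already known about the patient after that day. Here something often is: every patient in the efficacy population has a first dose, and most will have later visits. The rule does not use those dates, so it can place a death before a dose, scan or visit that the trial recorded.

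At stake are OS, and PFS and DOR where death is the event (SAP 6.2.3, 6.2.4 and Table 10). The death summary in SAP 6.3.2, which counts from the last dose, is also affected. SAP 5.2 says that outliers will be identified but that all data stay in the analysis, and nothing says what to do with a survival time of zero or less. Any repair would therefore be chosen after the data are seen.

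**Working it through.** The plan has no figure of its own to reproduce. The check applies the written rule to example dates, which are assumptions because the documents contain no patient-level dates.

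**Inputs.** Last-alive imputation and the one-day step: SAP 5.2. Survival formula: SAP 6.2.5, OS days = (death - first dose) + 1; months = days / 30.4375.

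**Month-only date, same month as first dose.** Imputed last-alive is the 1st and death the 2nd. With first dose on day *d* of the month, OS days = (2 - d) + 1 = 3 - d. This is 0 for d = 3 and negative from d = 4. For d = 20: 3 - 20 = -17 days; -17 / 30.4375 = -0.56 months.

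**Year-only date, same year as first dose.** Imputed death is 2 January, so OS is 0 for a first dose on 3 January and negative from 4 January on.

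**Share of first-dose days affected, given such a same-period partial date (365-day year).** Month-only: 365 - 12 × 3 = 329 days, or 90%. Year-only: 365 - 3 = 362 days, or 99%. These are conditional on the situation arising; they are not rates of occurrence.

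**Examples, as written and with the floor proposed under the fix.**

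| First dose | Last complete contact | Last-alive recorded as | Death as written | OS as written | Death with floor | OS with floor |
|---|---|---|---|---|---|---|
| 20 Mar 2020 | 20 Mar 2020 (the dose) | March 2020 | 2 Mar 2020 | -17 d (-0.56 mo) | 21 Mar 2020 | 2 d (0.07 mo) |
| 20 Mar 2020 | 14 Jul 2020 | July 2020 | 2 Jul 2020 | 105 d (3.45 mo) | 15 Jul 2020 | 118 d (3.88 mo) |
| 15 Sep 2020 | 10 Nov 2020 | 2020 | 2 Jan 2020 | -256 d (-8.41 mo) | 11 Nov 2020 | 58 d (1.91 mo) |
| 15 Sep 2020 | 10 Feb 2021 | 2021 | 2 Jan 2021 | 110 d (3.61 mo) | 11 Feb 2021 | 150 d (4.93 mo) |

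In all four rows the written rule dates death before the last complete contact; in two the survival time is negative. A floor at first dose alone would not be enough: in the third row it gives 16 September 2020 and 2 days, still before the 10 November visit.

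**Death summary.** Suppose the 14 July contact in the second row was the last dose. Death minus last dose is 2 - 14 = -12 days, which lies in none of the intervals counted after last dose in SAP 6.3.2.

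**Alternative parsing.** If the partial-date sentence is taken to set the death date itself, death falls one day earlier (first row: (1 - 20) + 1 = -18 days). The conclusion is the same.

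**The case against.** The best defence is that the last-alive date, in its ordinary sense, is the latest date on which anything shows the patient alive. Dose dates and times are recorded (protocol 6.7), and everyone in the efficacy population was dosed (SAP 4.2). A complete date therefore always exists, and the partial branch should seldom be reached.

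This stands as a limit on frequency. It does not close the gap. The SAP gives no derivation of the last-alive date and expressly provides for a partial one. The ordinary sense can also lead there: a patient seen on 14 July and later reported alive on an unspecified day in July has July 2020 as the latest information, and the rule then dates death to 2 July.

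Some stronger inferences are tempting, but the documents do not support them:

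- A reader might blame telephone survival follow-up. It starts only after the Day 100 end-of-treatment visit (Day 28 in some passages), so it cannot produce a partial date in the month of first dose. Nothing in the documents says that partial dates are commoner by telephone.
- A reader might say that such a death vanishes from the tables. SAP 6.3.2 also counts all deaths during the study, which still includes it; only the after-last-dose intervals miss it.
- A reader might put one patient at 4% of a curve, using 25. That number is for ORR precision (SAP 2.3). The primary efficacy analysis takes all dosed patients, about 30 per Phase 1b cohort.
- A reader might state what the Kaplan-Meier software does with a negative time. Neither document says.

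**Conclusion.** The point holds as a narrow defect in a stated rule. Applied literally, SAP 5.2 can date a death before a documented dose or visit, and in a narrower set of cases it gives an OS of zero or less.

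Zero or negative OS needs three things together: a wholly missing death date, a partial last-alive date, and that date falling in the month of first dose (or in the year, if only the year is known). A death dated before a documented contact needs only the first two, with the contact later in the same month or year. It should not be read as saying that negative survival times are likely; the documents give no basis for estimating how often this would occur, and I expect it to be rare.

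The effect is small. One patient is 1/30, or about 3%, of a cohort. All analyses are descriptive (protocol 9.0), and OS is not among the secondary endpoints listed in SAP Table 9. PFS and DOR are Phase 1b secondary endpoints, and the imputed date can reach them only when death is the event and Table 10 does not censor the patient first. The conclusion rests on reading the rule as written and on the absence of a last-alive derivation in the SAP.

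**What to change.** Change only the branch for a wholly missing death date. Suggested text:

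> If the last-alive date is partial, set it to the latest of (a) the first day of the known month or year, (b) the first dose date, and (c) the latest complete date on which the subject is documented alive (dose, visit, laboratory sample, scan or contact). Date the death to the following day.

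Item (a) has to stay. With a last visit on 14 July and last-alive October 2020, it keeps death at 2 October; using only the last complete date would pull it back to 15 July. The rules for partial death dates stay unchanged, and the new wording should sit inside the wholly-missing bullet so that it cannot be read as overriding them.

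The cost is one sentence in the SAP and a maximum-date check in the derivation program. No change to study conduct is needed.

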5.3 Data Handling Conventions and Transformations

In PK analysis, natural logarithm transformation will be used for serum concentration and analysis of PK parameters. Concentration values that are below the limit of quantitation (BLQ) will be presented as “BLQ” in the listing. Values that are BLQ will be treated as 0 at Cycle 1 Day 1 pre-dose timepoint, and treated as missing for other timepoints in the concentration summaries.

5.4 Definition of Baseline

When appropriate, baseline is defined as the last non-missing result with a collection date-time less than the date-time of the first dose of study medication.

For continuous measurements before the first dose, if multiple measurements occur on the same day, the last non-missing value will be considered as the baseline value. If these multiple measurements occur at the same time, the last non-missing value will be used as baseline. For categorical measurements before the first dose, if multiple measurements occur on the same day, the last non-missing value will be considered as the baseline value. If these multiple measurements occur at the same time or the time is not available, the last non-missing value will be considered as the baseline value.

Measurements occurred after first dose date will be considered post baseline values.

5.5 Analysis Visit Windows

5.5.1 Study Day Calculation

Study day relative to first dose will be calculated as: event date - first dose date in the study + 1 (if event date \geq first dose date in the study) and event date - first dose date in the study (if event date $<$ first dose date in the study).

5.5.2 Visit Windows

Visit windows are presented in the [Appendix 1](#) and [Appendix 2](#).

6 Statistical Analysis

6.1 Subject Information

Subject information data will be performed on the Safety Population, except the subject disposition summary and listing will be based on the Enrolled Population.

6.1.1 Subject Enrollment and Disposition

The number and percentage of patients for each of the following will be provided.

- Patients enrolled
- Patients who received study treatment
- Patients who completed the treatment
- Patients discontinued from treatment prematurely, overall and by reasons of discontinuation
- Patients who completed the study
- Patients discontinued from study, overall and by reasons of discontinuation
- Analysis populations

Listings will be provided for discontinued patients and patients completing the study. The summaries and listing will be based on all enrolled patients.

6.1.2 Protocol Deviations

A summary of the number and percentage of patients with protocol deviations by type of deviation will be provided. A listing of protocol deviations will be presented. All protocol deviations felt to be significant enough to impact the interpretation of the results will be presented in the data listings.

Possible protocol deviations will include but are not limited to:

- Violations of eligible criteria
- Disallowed medications or procedures
- Issues regarding informed consent form

6.1.3 Treatment Exposure and Compliance

6.1.3.1 Treatment Exposure

Descriptive statistics will be provided by treatment for the following

- Number of FPT155 Administered
- Cumulative dose (mg)
- Total duration of exposure to study drug (weeks)

Total duration of exposure to study drug (in weeks) will be defined as (last available dosing date – first dosing date + 21)/7, regardless of any temporary interruptions in study drug administration.

The number and percentage of subjects who have dose reduction, dose delay or interruption, and infusion interruption will be summarized with reasons.

Summaries of exposure will be performed with the safety population. A by-subject listing of study drug administration will be provided.

6.1.3.2 Treatment Compliance

The treatment compliance (%) and dose intensity (%) will be summarized. Compliance is defined as the sum of all numbers of doses administered across the treatment phase and divided by the planned numbers of doses for the patient for phase.

Compliance (%) = Actual numbers of doses received / Scheduled numbers of doses * 100%

Dose intensity is defined as actual total dosage received divided by planned total dosage. The planned total dosage is determined by the numbers of planned dosing visit*assigned dose level.

Intensity (%) = Actual doses received / Scheduled doses * 100%

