#### 4.1.1.5 Dose Escalation Within a Cohort

In Phase 1a dose escalation, intra-patient dose escalation will be permitted in patients enrolled at dose levels below 70 mg, provided:

- The patient did not experience a DLT
- All other AEs have recovered to Grade 1 or lower prior to dose escalation
- The patient may only dose escalate by a maximum of 1 dose level every 21 days and only after that dose level has cleared DLT review by the CRC (eg, a patient enrolled at 0.07 mg may escalate to 0.21 mg only after the 0.21 mg dose level has been cleared by the CRC).
- The patient cannot dose escalate beyond the 70 mg dose level

Intra-patient dose escalation will only be permitted after a discussion between the Sponsor and investigator, taking into account the overall safety experience, PK, and PD data available at the time of the request. Safety data from such patients will be reviewed as part of the overall safety and tolerability of FPT155.

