## 6.5 Method of Treatment Assignment

An Interactive Voice/Web Response System (IVRS/IWRS) will be used to assign patients to study treatment.

Patients in Phase 1a dose escalation will be sequentially assigned to dose levels at the time of enrollment, as described in Section 4.1.1.2. Patients in Phase 1a dose exploration will be assigned to the dose level and schedule selected based on the results of the Phase 1a dose escalation, as described in Section 4.2. Patients in Phase 1b dose expansion will be assigned to the dose level and schedule selected based on the results of Phase 1a, as described in Section 4.3.

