5.1 Subject Grouping

Subjects will be grouped according to the actual treatment they received. Subjects with the same dose level from the dose escalation and exploratory in Phase 1a for monotherapy and Phase 1a for combination will be combined for summary.

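### The planned-dosage denominator uses a single dose level, so dose intensity is wrong for Phase 1a patients who step up to a higher dose

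*SAP*

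**What the plan says.** SAP 6.1.3.2 gives the ratio: "Dose intensity is defined as actual total dosage received divided by planned total dosage". It then defines the denominator: "The planned total dosage is determined by the numbers of planned dosing visit*assigned dose level". Only one level enters the product.

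Protocol 6.5 says when that level is set: "Patients in Phase 1a dose escalation will be sequentially assigned to dose levels at the time of enrollment".

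Protocol 4.1.1.5 allows the level to change afterwards: "intra-patient dose escalation will be permitted in patients enrolled at dose levels below 70 mg, provided" certain conditions hold. On pace, "The patient may only dose escalate by a maximum of 1 dose level every 21 days", and only once the Cohort Review Committee (CRC) has cleared the higher level. On the ceiling, "The patient cannot dose escalate beyond the 70 mg dose level".

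The SAP does not mention this escalation. Its exposure section (6.1.3.1) counts reductions, delays and interruptions, but not step-ups. For by-dose displays, SAP 5.1 says only: "Subjects will be grouped according to the actual treatment they received". SAP 6.3.1.6 tabulates treatment-emergent events by treatment group, and 6.3.1.5 runs the event window through all treatment plus 100 days. Protocol 4.1.1.5 adds that safety data from escalated patients are reviewed within the overall safety assessment, which is not a tabulation rule.

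**The concern.** The numerator follows the doses actually given, while the denominator stays at the entry dose. A patient who escalates exactly as the protocol allows is therefore reported as over-dosed against plan. Because the levels rise by factors of 1.67 to 3.33, one such patient can dominate the mean of a cohort of one to six. No planned summary of step-ups would explain the value. The same mismatch can cancel real missed doses and make poor delivery look complete.

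The grouping rule has a related gap. A patient treated at several levels has no single actual treatment, so the programmer must choose a column for events that may have begun at any of those levels. AE incidence is a primary Phase 1a endpoint, and by-dose tables are one display of it.

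**Working it through.** **Inputs.** Dose levels in mg (Protocol Table 8): 0.07, 0.21, 0.70, 2.1, 7, 21, 42, 70. The formula is from SAP 6.1.3.2, the level at enrollment from Protocol 6.5, and the escalation conditions from Protocol 4.1.1.5. The documents state no dose-intensity figure, so there is none to reproduce.

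**Earliest step.** Protocol 4.1.1 takes escalation decisions after the last patient in a cohort completes 21 days. The next level therefore opens no earlier than about the end of a patient's first cycle, and needs at least 21 more days to clear. The first step falls at about cycle 3, so I assume two cycles at the entry dose. The paths below then take one level per cycle with no missed doses. They are fast paths, and slower escalation gives smaller figures.

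**Formula as written.** Intensity = sum of doses received / (visits × entry dose) × 100.

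- 42, 42, 70, 70: 224 / (4 × 42 = 168) = 133%
- 21, 21, 42, 70: 154 / (4 × 21 = 84) = 183%
- 0.07, 0.07, 0.21, 0.70, 2.1, 7: 10.15 / (6 × 0.07 = 0.42) = 2,417%

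The same pattern over six cycles, for every entry level:

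| Entry dose (mg) | Sum received (mg) | 6 × entry dose (mg) | Intensity |
|---|---|---|---|
| 0.07 | 10.15 | 0.42 | 2,417% |
| 0.21 | 31.22 | 1.26 | 2,478% |
| 0.70 | 73.5 | 4.2 | 1,750% |
| 2.1 | 144.2 | 12.6 | 1,144% |
| 7 | 217 | 42 | 517% |
| 21 | 294 | 126 | 233% |
| 42 | 364 | 252 | 144% |

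**Lower end.** One late step, with five of six cycles at entry and one at the next level, gives (5 + r)/6, where r is the ratio of the two levels. For 42 to 70 mg, r = 1.67 and the result is 111%. For 0.21 to 0.70 mg, r = 3.33 and the result is 139%. A 42 mg starter always stays below 70/42 = 167%.

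**Masking of missed doses.** Take a 42 mg starter with six planned visits, two at 42 mg and four at 70 mg, who misses one of each. Received: 42 + 3 × 70 = 252.

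- As written: 252 / (6 × 42 = 252) = 100%
- With the level assigned at each visit: 252 / (2 × 42 + 4 × 70 = 364) = 69%

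**After the fix.** Summing the level assigned at each visit makes every fully delivered path 100%. For the 0.07 mg starter, 10.15 / 10.15 = 100%.

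**Who could be affected.** Monotherapy cohorts 1aM1 to 1aM7, taking one patient in each of the four accelerated cohorts and three to six in each of the three 3+3 cohorts below 70 mg: 4 × 1 + 3 × 3 = 13 to 4 × 1 + 3 × 6 = 22. The same counting over all 13 cohorts gives 4 × 1 + 9 × 6 = 58, which matches the stated maximum.

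**The case against.** The best defence is that the assigned level could be read as the level re-assigned at each visit, in which case the formula works. SAP 6.1.3.2 does not say this, and Protocol 6.5 ties assignment to enrollment.

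It is also fair that much can be recovered elsewhere. SAP 6.1.3.1 reports cumulative dose and a by-subject administration listing, all AEs are listed, and the dose-count compliance measure is unaffected. For patients who never escalate, the formula is sound as written. These points limit the harm but do not make the intensity summary right.

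Two stronger readings should be resisted:

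- **Escalation from cycle 2.** A reader might step one level per cycle from cycle 2, so that eight cycles from 0.07 to 70 mg give 143.08 / 0.56 = 25,550%. The CRC clearance condition rules that path out.
- **Events credited to the wrong dose.** A reader might infer that the plan places higher-dose AEs under lower doses. SAP 5.1 names actual treatment, not entry dose. Entry-dose grouping would shift events downward and highest-dose grouping would shift them upward, and the text chooses neither. Nor is the last dose before onset plainly the correct attribution, since Protocol 2.4 itself notes delayed immune-mediated toxicity.

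**Conclusion.** The dose-intensity definition is wrong for patients who escalate within Phase 1a. The error ranges from modest (111% to 139% for one late step; below 167% for any 42 mg starter) to very large (over 1,000% on the fast six-cycle paths from 2.1 mg or below). It can also conceal missed doses. These results rest on the assigned level being the enrollment level and on assumed escalation paths. The documents do not say how many patients escalated, and the range of 13 to 22 counts those who could have, with one patient per accelerated cohort.

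The reach is limited. The 21-day DLT window precedes any step, so DLT summaries stand. Protocol 6.9.1 bars escalation in dose exploration and Phase 1b, and the 70 mg ceiling leaves levels of 140 mg and above untouched. Protocol Appendix 11 supports the 560 mg expansion dose by cumulative safety results, naming patients at 280 and 560 mg.

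The grouping point is an ambiguity to settle, not an established misattribution. Overall this is a minor point, worth correcting because the correction costs so little.

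**What to change.** **SAP 6.1.3.2.** Define planned total dosage as the sum, over planned visits, of the dose level assigned for that visit. State that an approved intra-patient escalation changes the assigned level from that visit on, that a missed visit carries the level then in force, and that a toxicity-related reduction leaves the planned level unchanged. Without the last clause, reductions would vanish from the measure. In 6.1.3.1, add a count of patients who escalated.

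**SAP 5.1.** State one grouping for subjects treated at several levels, for example entry dose, labelled as such in every by-dose table. Add a supplementary display of AEs by dose level at onset for these patients only. Present it as descriptive, and say how patients and exposure are counted in each column.

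**Cost.** A few sentences, one per-visit planned-dose variable and one extra display. No dosing rule, visit or data collection changes.
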